- Subjects with prior treatment for PCa including BT, RT or hormone therapy.

c) Number of Subjects:

This is a 3+3 dose escalation design study to determine the MTD. This study will use 2 dose levels and 1-6 subjects at each dose level. The first subject enrolled at each dose level (60 and 75 Gy) will be monitored for the entire DLT window (3 months post EBRT completion) with subsequent subjects enrolled either at the same dose (if only 1 of the first 3 subsequent subjects at the given dose experiences DLT) or in the

[Type here]

Protocol Title:	A Phase I Single-Arm Open Label Dose-Escalation Study of CivaSheet with Radical Prostatectomy with or without Adjuvant External Beam Radiation Therapy in Patients with High Risk Prostate Cancer
Principal Investigator Name/Contact Info:	[name]/ [contact]/ [contact]
Primary Contact Name/Contact Info	[contact] [name]
Date Revised:	7/22/2022
Study Number:	GCO#1: 16-1314

next dose level if the preceding dose is deemed acceptable (i.e., < 33% DLT within 90 days post EBRT). If in the first subject, Grade 4-5 hematuria, fistula formation, proctitis or death occurs in the DLT window, the trial will be terminated. The total number of subjects for this single arm 3+3 trial design is therefore a minimum of 1 and a maximum of 12.

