The dose escalation design utilized for the present study will proceed as follows: The first subject will be enrolled at 60 Gy. Once the entire DLT window (i.e., 90 days post EBRT) is complete for this first subject, the next 2 subjects will be enrolled at 60 Gy. If in the first subject, grade 4 or higher hematuria, proctitis, fistula formation or death occurs in the DLT window, the trial will be terminated. If 2 of the first 3 subjects experience DLT at 60 Gy, the trial will be terminated. If 0 or 1 of the first 3 subjects enrolled at 60 Gy experience a DLT after the third subject's entire DLT window is complete, an additional three subjects will be enrolled at 60 Gy. If $\geq 33\%$ of subjects experience DLT at 60 Gy, the trial will be terminated. If after the sixth subject's DLT window is complete and < 33% of subjects experience DLT at 60 Gy, the first subject at 75 Gy will be enrolled. Once the entire DLT window (i.e., 90 days post EBRT) is complete for this first subject at 75 Gy, the next two subjects will be enrolled at 75 Gy. If in the first subject at 75 Gy, grade 4 or higher hematuria, fistula formation, proctitis or death occurs in the DLT window, 60 Gy will be considered the MTD and no additional subjects will be enrolled at 75 Gy. If 2 of the first 3 subjects experience DLT at 75 Gy, 60 Gy will be considered the MTD and no additional subjects will be enrolled at 75 Gy. If 1 or 0 of the first 3 subjects enrolled at 75 Gy experience a DLT after the third subject's entire DLT window is complete, an additional 3 subjects will be enrolled at 75 Gy. If $\geq 33\%$ of subjects experience DLT at 75 Gy, no additional subjects will be enrolled at 75 Gy and 60 Gy will be considered the MTD. If after the sixth subject's DLT window is complete and < 33% of subjects experience DLT at 75 Gy, 75 Gy will be considered the MTD.

The true risk of toxicity is expected to be in the range of 10-50%. The following table shows the corresponding probabilities of dose escalation.

True Risk of Toxicity	0.1	0.2	0.3	0.4	0.5
Probability of Escalation	0.96	0.87	0.69	0.50	0.31

[Type here]

Protocol Title:	A Phase I Single-Arm Open Label Dose-Escalation Study of CivaSheet with Radical Prostatectomy with or without Adjuvant External Beam Radiation Therapy in Patients with High Risk Prostate Cancer
Principal Investigator Name/Contact Info:	[name]/ [contact]/ [contact]
Primary Contact Name/Contact Info	[contact] [name]
Date Revised:	7/22/2022

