Study Number:	GCO#1: 16-1314

A minimum of 3 and a maximum of 6 subjects within a dose level must be observed for one cycle (90 day post EBRT completion) before accrual to the next higher dose level may begin.

Three patients within a dose level must be observed for one cycle (30 days post EBRT) before accrual to the next higher dose level may begin. The treatment for this study is RP + Civasheet implant + adjuvant EBRT for patients with high-risk or intermediate (non-clinically localized) prostate cancer with adverse pathologic features including seminal vesicle invasion, extra prostatic extension or a positive surgical margin. Since the clinical guidelines recommend adjuvant EBRT post RP only for patients with adverse pathologic features at RP, patients without these adverse pathologic features at RP will be replaced with additional patients at that dose level. Since however eligibility criteria is for high risk or non-clinically localized intermediate risk prostate cancer, the anticipated number of patients without these adverse pathologic features who will not receive adjuvant EBRT is 2 or less. While toxicities among these patients will be monitored according to the protocol, toxicities among these patients will not be used in determinations of the MTD. The MTD will only be determined for patients undergoing RP + Civasheet implant + adjuvant EBRT.

If a subject is withdrawn from the study prior to completing the entire cycle of therapy or prior to completing the entire DLT window without experiencing a DLT prior to withdrawal, an additional subject may be added to that dose level. Subjects missing doses due to a DLT will not be replaced since these subjects will be considered to have experienced a dose limiting toxicity.

d) Study Timelines:

The duration of an individual subject's participation in this study including follow-up is 5 years.

The expected duration for the investigators to complete this ranges between 1 month for a minimum of 1 subject and 44 months for a maximum of 12 subjects.

Table 1. Time and events table for those undergoing RP + Civasheet implant + adjuvant EBRT.

[Type here]

Effective Date: 10/18/2022

End Date: 10/17/2023

Protocol Title:	A Phase I Single-Arm Open Label Dose-Escalation Study of CivaSheet with Radical Prostatectomy with or without Adjuvant External Beam Radiation Therapy in Patients with High Risk Prostate Cancer									
Principal Investigator Name/Contact Info:	[name]/ [contact]/ [contact]									

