Primary Contact Name/Contact Info	[contact] [name]									
Date Revised:	7/22/2022									
Study Number:	GCO#1: 16-1314									

	Pre-study	Day 1	Discharge (Typically Day 2)	1 Week	1 Month	6 Weeks	12 Weeks	23 Weeks	35 Weeks	Routinely for 4 years after Study completion
Assessment	X	X	X	X	X	X	X	X	X	X
Informed Consent, AE, Medical History/Medication s, Eligibility criteria, Pre-Surgical clearance (i.e., chest, EKG, etc.).	X									
Toxicity/ AE/ Complications (including DLT) Evaluations		X	X	X	X	X	X	X	X	X
X-Ray	X									
CBC	X	X	X							
Other required labs (PSA, testosterone, BMP)	X	X	X	X			X	X	X	
IIEF	X			X	X			X	X	X
MRI	X									
CT Scan			X		X		X		X	
Radical Prostatectomy + Civasheet Implant		X								
EBRT for 5 weeks						X				

Table 2. Time and events table for those undergoing RP + Civasheet implant without adjuvant EBRT.

	Pre-	Day	Discha	1	1	Routinel

[Type here]

Effective Date: 10/18/2022

End Date: 10/17/2023

Protocol Title:	A Phase I Single-Arm Open Label Dose-Escalation Study of CivaSheet with Radical Prostatectomy with or without Adjuvant External Beam Radiation Therapy in Patients with High Risk Prostate Cancer					
Principal Investigator Name/Contact Info:	[name]/ [contact]/ [contact]					
Primary Contact Name/Contact Info	[contact] [name]					
Date Revised:	7/22/2022					
Study Number:	GCO#1: 16-1314					

	study	1	age (Typically Day 2)	Week	Month	Year for 4 years after Study completion
Assessment	X	X	X	X	X	X
Informed Consent, AE, Medical History/Medication s, Eligibility criteria, Pre-Surgical clearance (i.e., chest, EKG, etc.).	X					
Toxicity/ AE/ Complications (including DLT) Evaluations		X	X	X	X	X
X-Ray	X					
CBC	X	X	X			
Other required labs (PSA, testosterone, BMP)	X	X	X	X		X
IIEF	X			X	X	X
MRI	X					
CT Scan			X		X	
Radical Prostatectomy + Civasheet Implant		X				

Assessments performed exclusively to determine eligibility for this study will be done only after obtaining informed consent. Assessments performed for clinical indications (not exclusively to determine study eligibility) may be used for baseline values even if the studies were done before informed consent was obtained.

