90 Days after Completion of EBRT

- Assessment of cumulative DLT's to decide whether progression to next dose or termination of study is necessary.

Follow-Up:

- Subjects will be followed every 6 months after completion of study treatment for 4 years or if the subject withdraws consent from participation, the subject will not be followed-up. Subjects may be followed-up by telephone or contacted by phone to schedule Mount Sinai office visits to monitor for cancer recurrence and or cancer progression in addition to late toxicity.
- Subjects will be followed yearly after completion of study treatment for 4 years or if the subject withdraws consent from participation, the subject will not be followed-up. Subjects may be followed- up by telephone or contacted by phone to schedule Mount Sinai office visits to monitor for cancer recurrence and or cancer progression in addition to late toxicity.
- If patients are not scheduled for their follow-up visits with Mount Sinai Health System, the study team will call the patient to schedule a visit.
 - If the patient schedules a follow-up at Mount Sinai, appropriate measures will be assessed according to the protocol and data will be recorded.
- If the patient is seeing a physician outside of Mount Sinai Health System, we will request that their labs and physician notes are sent to us.
 - A research coordinator will review and record the outside labs and contact the patients to collect any missing information that can be obtained by phone (i.e. bleeding, incontinence, etc.)
 - A symptomology follow-up form, as well as an IIEF assessment form are attached.
 - If additional information is necessary to assess DLTs or AEs, a coordinator will call the patient and request they schedule a follow up visit at Mount Sinai. If the patient is unable to come in for a follow-up visit, they will be dropped the study.
 - If patients are not responsive after 2 attempts, they will be considered lost to follow up and replaced.

For those with adverse pathologic features: At 1 week post RP+ Civasheet

[Type here]

Protocol Title:	A Phase I Single-Arm Open Label Dose-Escalation Study of CivaSheet with Radical Prostatectomy with or without Adjuvant External Beam Radiation Therapy in Patients with High Risk Prostate Cancer
Principal Investigator Name/Contact Info:	[name]/ [contact]/ [contact]
Primary Contact Name/Contact Info	[contact] [name]
Date Revised:	7/22/2022
Study Number:	GCO#1: 16-1314

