implant, 6 weeks after EBRT, 3 months after EBRT and 6 months after EBRT during the clinic visits, subjects will complete the IIEF to assess baseline erectile function following treatment. Subjects will undergo PSA testing for each follow-up visit. Those without adverse pathologic features not undergoing adjuvant EBRT will complete the IIEF to assess baseline erectile function following treatment and will also undergo PSA testing for each follow-up visit. Also at each follow-up visit or telephone follow up, subjects will be screened for toxicity and complications. The assessments may be done by phone when possible or lab results may be sent by the patient to our EMR if patient has followed up with an outside physician. For all patients, a CT-scan at day 0 (RP+Civasheet implant) will be done for a baseline stability assessment of the Civasheet. For all patients, a one month post-implant CT scan will be done of the pelvis for three purposes. The first purpose will be to perform a post-implant dosimetric analysis of the implanted Civasheet®. The bladder, rectum and any other identifiable structures (small bowel, large bowel or lymph nodes) will be outlined. The delivered dose will be calculated using a dose volume histogram and recorded. The second part of the CT will be to design the post-implant external beam radiation field among those who will undergo adjuvant EBRT. The third part will be to assess the stability of the Civasheet and any changes in position from initial implant. Among those who will undergo adjuvant EBRT, an additional post-implant CT scan at 90 days and 6 months will be done of the pelvis to prove stability of the device/implant method and to assess for cancer recurrence while those not undergoing adjuvant EBRT will not receive this imaging at 90 days and 6 months.

e) Specimen Banking for Future Uses Not Part of This Project:

NA

f) Data Storage, Transmission and Confidentiality:

To ensure data accuracy and completeness, random checks will be done by members of the research team listed in the protocol who are not directly responsible for data collection and entry. Data irregularities and errors will be collected and reported to the . Data collected and stored for current and future research use will include age, gender, [type here]

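### The protocol sets the observation period before escalation at both 90 and 30 days after EBRT; the 30-day sentence should go

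*Protocol*

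**What the plan says.** Two consecutive sentences in Protocol section 3(c), Number of Subjects, govern when accrual at the next dose may start. The first asks that three to six "subjects within a dose level must be observed for one cycle (90 day post EBRT completion" has passed. The second reads "Three patients within a dose level must be observed for one cycle (30 days post EBRT) before accrual to the next higher dose level". Both call the period one cycle.

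Elsewhere the period is 90 days or 3 months:

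- Earlier in section 3(c), an acceptable dose is one with "< 33% DLT within 90 days post EBRT".
- The escalation algorithm in section 3(c) releases the next 60 Gy subjects "Once the entire DLT window (i.e., 90 days post EBRT) is complete for this first subject".
- Under the heading for 90 days after completion of EBRT, the planned action is "Assessment of cumulative DLT's to decide whether progression to next dose or termination of study is necessary".
- The safety-monitoring text and the Stopping Rules in the Protocol, and the Primary Outcome section of the SAP, all use 90 days.

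**The concern.** A dose-escalation gate should have one period, equal to the window over which dose-limiting toxicity is counted. Here the same gate, described with the same term, has two.

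If staff relied on the 30-day sentence, a 75 Gy sheet could be implanted up to 60 days before the DLT window closes for the latest 60 Gy subjects. A DLT on days 31 to 90 would still be recorded and would still count under the Stopping Rules, which close the trial at 33% or more. But section 16 describes the sheet as permanently implanted, so closing the trial would not reverse the exposure of a subject already treated at 75 Gy.

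**Working it through.** **1. Which period is the outlier**

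| Place | Period after EBRT |
|---|---|
| Protocol 3(c), DLT window for the first subject at each dose | 3 months |
| Protocol 3(c), escalation algorithm | 90 days |
| Protocol 3(c), first cycle sentence | 90 days |
| Protocol 3(c), second cycle sentence | **30 days** |
| Protocol, escalation decision point | 90 days |
| Protocol, safety-monitoring text | 90 days |
| Protocol, Stopping Rules | 90 days |
| SAP, Primary Outcome | 90 days |

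Other 30-day periods in the Protocol concern screening and eligibility, the post-implant CT, and adverse-event reporting. None concerns DLT or escalation.

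**2. Calendar**

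Inputs: EBRT starts 6 weeks after prostatectomy and lasts 5 weeks (SAP, Primary Outcome).

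- End of EBRT: 42 + 35 = day 77 (week 11).
- Day 30 after EBRT: 77 + 30 = day 107; 107/7 = week 15.3.
- Day 90 after EBRT: 77 + 90 = day 167; 167/7 = week 23.9.

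**3. Visits near each date**

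The Table 1 row "Toxicity/ AE/ Complications (including DLT) Evaluations" has entries at weeks 12 and 23, with none between. The Follow-Up text also lists "6 weeks after EBRT, 3 months after EBRT and 6 months after EBRT during the clinic visits".

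- Week 12: 84 − 77 = 7 days after EBRT.
- Follow-up visit 6 weeks after EBRT: day 42 after EBRT, that is week 17.
- Week 23: 161 − 77 = 84 days after EBRT.

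The last scheduled evaluation before day 30 is therefore about 7 days after EBRT, and the next is at day 42 or day 84. Week 23 is 6 days short of day 90.

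**4. Size of the difference**

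- 90 − 30 = 60 days; 60/90 = two-thirds of the DLT window.
- There is one escalation step, so at most 60 days are saved, once: 60/30.44 = 1.97 months.
- As a share of the planned maximum: 1.97/44 = 4.5%.

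**5. Does the planned duration accommodate 90 days?**

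Section 3(d) gives "44 months for a maximum of 12 subjects" without a derivation, so the figure cannot be reproduced. The longest path in the section 3(c) algorithm is six successive cohorts (1, 2 and 3 subjects at each of two doses). Assume that each cohort is enrolled together, with no accrual gaps and no replacements.

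- With 90 days: 6 × 167 = 1,002 days; 1,002/30.44 = 32.9 months. This leaves 44 − 32.9 = 11.1 months for accrual and replacements.
- With 30 days throughout: 6 × 107 = 642 days; 642/30.44 = 21.1 months.

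Both fit. The stated duration shows that 90 days is feasible, but it does not show which period was intended.

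**6. The escalation table**

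The tabulated probabilities of escalation in section 3(c) have no time input. They reproduce to within 2 percentage points from a rule that escalates on 0 of 3, or on 1 of 3 followed by at most 1 of the next 3. At a true risk of 0.3:

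0.343 + 0.441 × (0.343 + 0.441) = 0.689, against 0.69 stated.

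Removing the 30-day sentence leaves the table unchanged. The effect of a shorter window would depend on the share of 90-day DLTs that appear by day 30, which the documents do not give.

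**The case against.** The strongest reply is that the text, read as a whole, never permits escalation at day 30. Both sentences are necessary conditions, and meeting the 90-day one meets the 30-day one. The algorithm enrols the first 75 Gy subject only after the sixth 60 Gy subject's DLT window is complete, and the decision point is fixed at 90 days. Staff would have to overlook all of this to cause harm. That is right, and it limits the point to ambiguity. It does not make the sentence harmless, because it sits in the operative safety rule and states a wrong threshold.

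The visit schedule is only supporting evidence. Toxicity is also assessed by telephone and whenever a subject is seen, and Table 1 has no visit exactly at day 90. Even so, week 23 is within a week of day 90, while nothing is scheduled at day 30.

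Deletion also removes a statement about three patients. The preceding sentence keeps a minimum of three, so the count required by this pair of sentences is unchanged. The wider disagreement on counts is real but separate: the algorithm requires six subjects, while the safety-monitoring text allows escalation after three with no DLT. This fix does not settle it.

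**Conclusion.** The concern holds and should be fixed. Two current sentences give the same gate periods that differ by 60 days, and the 30-day figure contradicts every other statement of the window. The defect is an ambiguous gate, not an instruction to escalate early. Relying on the shorter period would leave two-thirds of the DLT window unobserved in the latest 60 Gy subjects, to save at most 2.0 of 44 months. No change in the probability of escalation is claimed. The calendar assumes EBRT in weeks 6 to 11 as planned, and the 32.9-month path assumes no accrual gaps or replacements.

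**What to change.** Delete the second cycle sentence in Protocol section 3(c), so that 90 days after completion of EBRT is the only observation period before accrual at 75 Gy. Changing 30 to 90 in that sentence would serve equally well for the period.

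Leave the 30-day period for notifying serious adverse events under Reporting Requirements as it is, because it serves another purpose. Resolve the number of subjects required before escalation separately, together with the escalation table.

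The cost is one sentence in a protocol amendment. Sample size and visits do not change, and the 90-day path fits within the planned 44 months under the assumptions above.

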race, height, weight, , study information (subject study ID), medical history (allergies, other illnesses, symptoms at presentation, medications, prior surgery), physical examination information (Whole body physical exam including related to the rectal exam for prostate cancer screening) information related to prostate cancer (pathology from biopsy and surgery), any imaging data pertaining to prostate cancer (CT, MRI, ultrasound, bone scan), blood tests done as part of cancer work up (PSA, testosterone – total and free), procedural data (prostatectomy, external beam radiation therapy if necessary), and responses to all study related questionnaires (the International index of erectile function questionnaire), follow-up data including blood work, questionnaires, imaging. Subject data collected will be associated with unique study numbers and to connect each subject with their clinical data. Data excluding names, social security numbers, hospital record numbers, address [mailing and email], phone numbers, fax numbers, account numbers, health plan number will be stored on a secure computer in the PI's locked office or kept in REDCap (Research Electronic Data Capture), a secure web application. REDCap is a project creation tool to build and manage online clinical databases and to collect and manage online clinical data. REDCap provides audit capabilities to track researchers' use of the platform. Data will be stored indefinitely. All study data at Mount Sinai stored electronically will follow MSMC policies. All PHI not stored in the database will be encrypted and password protected. The key to the identification number to connect subjects with their clinical data will also be kept in REDCap and on a secured computer in the PI's locked office. The PI is responsible for receipt or transmission of the data. All research team members listed on this protocol will have access to the data with identifiers during the conduct of the trial. Data will only be used by these team members in the PI's locked office. Data will be transmitted for use only on a secured server having password protected access by only research personnel listed on this protocol.

Date Revised:	7/22/2022
Study Number:	GCO#1: 16-1314

research. He serves as an editor and/or reviewer for numerous publications including Cancer, Journal of Urology, Urologic Oncology, Journal of Endourology, among others.

The Principal Investigator is responsible for the conduct of the clinical trial at the site in accordance with Title 21 of the Code of Federal Regulations and/or the Declaration of Helsinki. The Principal Investigator is responsible for personally overseeing the treatment of all study subjects. The Principal Investigator will assure that all study site personnel, including sub-investigators and other study staff members, adhere to the study protocol and all FDA/GCP/NCI regulations and guidelines regarding clinical trials both during and after study completion. Except for an emergency situation in which proper care for the protection, safety, and well-being of the study subject requires alternative treatment, the study shall be conducted exactly as described in the approved protocol.

Investigators may implement a deviation from, or a change of, the protocol to eliminate an immediate hazard(s) to trial subjects without prior IRB approval.

The Principal Investigator at each institution or site is responsible for assuring that all the required data will be collected and entered onto the Case Report Forms. Periodically, monitoring visits will be conducted and the Principal Investigator will provide access to his/her original records to permit verification of proper entry of data. At the completion of the study, all case report forms will be reviewed by the Principal Investigator and his required final signature will verify the accuracy of the data

Adverse events, complication, toxicity and subject compliance with the protocol will be monitored. Adverse events related to surgery will be graded using the Dino-Clavien grading system. As per standard care, standard side effects of surgery including but not limited to fever, chills, nausea, vomiting, abdominal pain, constipation, incontinence will be monitored and appropriate therapy implemented. The adverse events for surgery we monitor include infection, stricture, abscess, bowel perforation, erosion into surrounding structures, bleeding, fistula, worse rates of continence and erectile function. Adverse events and toxicity associated with radiation we monitor include GI and GU toxicity, bladder and rectal adverse effects, urethral strictures, hematuria, radiation proctitis. All toxicity will be graded according to the RTOG acute and late morbidity scoring schemes. The adverse events related to the implementation of the Civasheet® include radiation to other areas due to movement of the sheet which will be monitored with a 30 day post implant CT to ensure stability of the device and implant method for all patients and additionally at 90 days and at 6 months for those undergoing EBRT. To ensure subject compliance, subjects will be counseled each visit or phone call as on the adherence to study criteria. Subject failure to follow up or comply with protocol as well as the reasons for failure to follow up or comply with protocol will be assessed and documented.

Type here]

Protocol Title:	A Phase I Single-Arm Open Label Dose-Escalation Study of CivaSheet with Radical Prostatectomy with or without Adjuvant External Beam Radiation Therapy in Patients with High Risk Prostate Cancer
Principal Investigator Name/Contact Info:	[name]/ [contact]/ [contact]
Primary Contact Name/Contact Info	[contact] [name]
Date Revised:	7/22/2022
Study Number:	GCO#1: 16-1314

Adverse events and toxicity will be monitored and assessed at each follow-up visit or phone call for all subjects enrolled. After the first subject's DLT window is complete at 60 Gy (90 days post-EBRT), we will make a decision to enroll additional subjects at 60 Gy only if Grade 4-5

hematuria, proctitis, or fistula are not observed. If 2 additional subjects are enrolled at 60 Gy, we will review for DLTs after completion of the 90 day DLT window and enroll 3 additional subjects at 60 Gy if DLT has been observed in 1 subject, or enroll 1 subject at 75 Gy if no DLT were observed or terminate the trial if $\geq 33\%$ DLT were observed in all subjects. For the next group of subjects at 60 Gy, we will review DLT/toxicity after all three subjects have completed the 90 days DLT window after EBRT. After the first subject's DLT window is complete (90 days post-EBRT) at 75 Gy, we will make a decision to enroll additional subjects at 75 Gy only if Grade 4-5 hematuria, proctitis, or fistula are not observed. If 2 additional subjects are enrolled at 75 Gy, we will review for DLTs after completion of the 90 day DLT window and enroll 3 additional subjects at 75 Gy if DLT has been observed in 1 subject, or terminate the trial if $\geq 33\%$ DLT were observed among the first three subjects at 75 Gy. For the next group of three subjects at 75 Gy, we will review DLT/toxicity after all three subjects have completed the 90 days DLT window. We will additionally describe rates of complications and toxicity (i.e., acute and late overall, GU and GI) by grade and by dose once the 6 month follow-up period is complete for all subjects. Toxicities among those not receiving EBRT will not affect the MTD determination or the decision to enroll additional patients at the same dose or at a higher dose. The DMC will review data at least once annually.

If the DMC recommends termination of the study we will terminate the study. If in the first subject at any dose Grade 4-5 hematuria, proctitis or fistula occur, we will terminate the study. If $\geq 33\%$ of subjects experience DLT (i.e., Grade 3 hematuria, proctitis, urinary retention) within the first 90 days post EBRT, the trial will be closed.

The Clavien-dindo classification of surgical complications will be used to assess complications and the NCI-CTCAE v4.0 in addition to the RTOG acute and late morbidity scoring criteria will be used to grade adverse events and toxicity.

Should a temporary or permanent suspension of our study occur, we will report the occurrence to the IRB and CivaTech Oncology®. If terminated, we will inform the IRB and research offices of termination. If terminated, we will continue to offer the standard of care for study subjects. If study termination is due to safety concerns, we will inform subjects by phone, mail or email of the study's status. If terminate not due to safety concerns, we will inform subjects during routine clinical visits.

The study will use the DSMC of the TCI as the data monitoring committee. All unexpected adverse events will be presented to the DSMB for review. All recommendations of the DSMB will be followed and implemented. If a situation arises in which the DSMC recommends termination of the study, we will terminate the study. To ensure data accuracy and completeness, random checks will be done by members of the search team listed in the protocol who are not directly responsible for data collection

[Type here]

Protocol Title:	A Phase I Single-Arm Open Label Dose-Escalation Study of CivaSheet with Radical Prostatectomy with or without Adjuvant External Beam Radiation Therapy in Patients with High Risk Prostate Cancer
Principal Investigator Name/Contact Info:	[name]/ [contact]/ [contact]
Primary Contact Name/Contact Info	[contact] [name]
Date Revised:	7/22/2022
Study Number:	GCO#1: 16-1314

and entry. Data irregularities and errors will be collected and reported to the PI. Should a temporary or permanent suspension of our study occur, we will report the occurrence to the IRB and MiMedx®. This study will use of the Tisch Cancer Center as the data monitoring committee. If notable safety issues are found in our interim analysis, the study will be interrupted as per DSMB recommendations. DSMB recommendations will be followed and implemented.

Study documentation includes all Case Report Forms, data correction forms or queries, source documents, Sponsor-Investigator correspondence, monitoring logs/letters, and regulatory documents (e.g., protocol and amendments, IRB correspondence and approval, signed subject consent forms).

Source documents include all recordings of observations or notations of clinical activities and all reports and records necessary for the evaluation and reconstruction of the clinical research study.

The study investigator will retain all study documentation pertaining to the conduct of a clinical trial according to government agency regulations and directives. Study documents will be kept on file until three years after the completion and final study report of this investigational study.

ADVERSE EVENTS

- Adverse Event Monitoring

Adverse event data collection and reporting will be done to ensure the safety of subjects enrolled in this study as well as those who will enroll in future studies using similar agents.

Adverse events will be reported in a routine manner at scheduled times during this trial. Additionally, certain adverse events will be reported in an expedited manner to allow for optimal monitoring of subject safety and care.

All subjects experiencing an adverse event, regardless of its relationship to study drug, will be monitored until:

- the adverse event resolves or the symptoms or signs that constitute the adverse event return to baseline;
- any abnormal laboratory values have returned to baseline;

[Type here]

Protocol Title:	A Phase I Single-Arm Open Label Dose-Escalation Study of CivaSheet with Radical Prostatectomy with or without Adjuvant External Beam Radiation Therapy in Patients with High Risk Prostate Cancer
Principal Investigator Name/Contact Info:	[name]/ [contact]/ [contact]
Primary Contact Name/Contact Info	[contact] [name]
Date Revised:	7/22/2022
Study Number:	GCO#1: 16-1314

- there is a satisfactory explanation other than the study drug for the changes observed; or
- death.

- **Definition of Adverse Event**

An adverse event (AE) is defined as any untoward medical occurrence in a subject receiving study treatment and which does not necessarily have a causal relationship with this treatment. An AE can therefore be any unfavorable and unintended sign (including an abnormal laboratory finding), symptom, or disease temporally associated with the use of an experimental intervention, whether or not related to the intervention.

- **Severity of Adverse Events**

All non-hematologic adverse events will be graded according to the NCI Common Terminology Criteria for Adverse Events (CTCAE) version 4.0. The CTCAE v4 is available at <http://ctep.cancer.gov/reporting/ctc.html> and will also rely on the radiation therapy oncology group's (RTOG) late and acute radiation morbidity criteria for assessing toxicity available at https://en.wikibooks.org/wiki/Radiation_Oncology/Toxicity_grading/RTOG

If no CTCAE grading is available, the severity of an AE is graded as follows:

Mild (grade 1): the event causes discomfort without disruption of normal daily activities.

Moderate (grade 2): the event causes discomfort that affects normal daily activities.

Severe (grade 3): the event makes the subject unable to perform normal daily activities or significantly affects his/her clinical status.

Life-threatening (grade 4): the subject was at risk of death at the time of the event.

Fatal (grade 5): the event caused death.

- **Serious Adverse Events**

[Type here]

Protocol Title:	A Phase I Single-Arm Open Label Dose-Escalation Study of CivaSheet with Radical Prostatectomy with or without Adjuvant External Beam Radiation Therapy in Patients with High Risk Prostate Cancer
Principal Investigator Name/Contact Info:	[name]/ [contact]/ [contact]
Primary Contact Name/Contact Info	[contact] [name]
Date Revised:	7/22/2022
Study Number:	GCO#1: 16-1314

A “serious” adverse event is defined in regulatory terminology as any untoward medical occurrence that:

* Results in death.

If death results from (progression of) the disease, the disease should be reported as event (SAE) itself.

* Is life-threatening.

(the subject was at risk of death at the time of the event; it does not refer to an event that hypothetically might have caused death if it were more severe).

* Requires in-subject hospitalization or prolongation of existing hospitalization for \geq 24 hours.

* Results in persistent or significant disability or incapacity.

* Is a congenital anomaly/birth defect

* Is an important medical event

Any event that does not meet the above criteria, but that in the judgment of the investigator jeopardizes the subject, may be considered for reporting as a serious adverse event. The event may require medical or surgical intervention to prevent one of the outcomes listed in the definition of “Serious Adverse

Event“.

- Steps to Determine If an Adverse Event Requires Expedited Reporting

Step 1: Identify the type of adverse event using the NCI Common Terminology Criteria for Adverse Events (CTCAE v4).

Step 2: Grade the adverse event using the NCI CTCAE v4.

Step 3: Determine whether the adverse event is related to the protocol therapy

Attribution categories are as follows:

- Definite – The AE is clearly related to the study treatment.
- Probable – The AE is likely related to the study treatment.
- Possible – The AE may be related to the study treatment.

[Type here]

Protocol Title:	A Phase I Single-Arm Open Label Dose-Escalation Study of CivaSheet with Radical Prostatectomy with or without Adjuvant External Beam Radiation Therapy in Patients with High Risk Prostate Cancer
Principal Investigator Name/Contact Info:	[name]/ [contact]/ [contact]
Primary Contact Name/Contact Info	[contact] [name]
Date Revised:	7/22/2022
Study Number:	GCO#1: 16-1314

- Unrelated – The AE is clearly NOT related to the study treatment.

Note: This includes all events that occur within 30 days of the last dose of protocol treatment. Any event that occurs more than 30 days after the last dose of treatment and is attributed (possibly, probably, or definitely) to the agent(s) will also be reported accordingly.

Step 4: Determine the prior experience of the adverse event.

Expected events are those that have been previously identified as resulting from administration of the agent. An adverse event is considered unexpected, for expedited reporting purposes only, when either the type of event or the severity of the event is not listed in:

- the current known adverse events listed in the Agent Information Section of this protocol;
- the drug package insert;
- the current Investigator's Brochure

- Reporting Requirements for Adverse Events

Expedited Reporting

- The Principal Investigator will be notified within 24 hours of learning of any serious adverse events, regardless of attribution, occurring during the study or within 30 days of the last administration of EBRT.
- Expedited reporting to Civatech Oncology is not required for adverse events.
- The IRB/PPHS will be notified within 5 business days of “any unanticipated problems involving risk to subjects or others” (UPR/UPIRSO).

- The following events meet the definition of UPR

- a. Any new information that indicates a new or increased risk, or safety issue (e.g., interim analysis, safety monitoring report, publication, updated sponsor safety report), that indicates an unexpected change to the risk/benefit ratio for the research.

[Type here]

Protocol Title:	A Phase I Single-Arm Open Label Dose-Escalation Study of CivaSheet with Radical Prostatectomy with or without Adjuvant External Beam Radiation Therapy in Patients with High Risk Prostate Cancer
Principal Investigator Name/Contact Info:	[name]/ [contact]/ [contact]
Primary Contact Name/Contact Info	[contact] [name]
Date Revised:	7/22/2022
Study Number:	GCO#1: 16-1314

